4.1. Overall Design

[figure not shown]
Study J1A-MC-KDAF (KDAF) is a Phase 2b, randomized, double-blind, placebo-controlled study to determine the appropriate dose and dosing frequency of peresolimab in adult participants with moderately-to-severely active RA.

This study includes a

- screening period
- CC double-blind, placebo-controlled treatment period
- CCl double-blind treatment period, and
- post-treatment follow-up.

See the SoA for visit schedule, procedural and assessment details (Section 1.3).

Participant population

Treatment period design

Follow-up period

Two follow-up visits occur at **CC** after the final treatment period visit.

Participation in an open-label extension study

If an open-label extension study is enrolling at the time the participant completes CCl they will be given the opportunity to enroll in that study.

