- How to account for ICEs: ICEs will be accounted using the same estimand strategy as for the primary estimand.
- Population-level summary: Proportion of participants achieving response at Week 24 (or Week 60) in each dosing regimen of peresolimab
- Rationale for estimand: Refer to the rationale for the primary estimand.

Secondary estimand for continuous endpoints at Week 24 and Week 60

For secondary objectives that have continuous endpoints analyzed at Week 12, the clinical question of interest is:

What is the average change from baseline to Week 24 (or Week 60) in the target patient population if all participants continued with treatment for 12 weeks without use of rescue or prohibited medications?

The estimand is described by the following attributes:

- Population: Participants with moderately-to-severely active RA
- Endpoint(s): Change from baseline for DAS28-hsCRP, SDAI, CDAI, TJC68, SJC66, and Physician's Global Assessment of Disease Activity (VAS) at Week 24 (or Week 60)

- How to account for ICEs: ICEs will be accounted using the same estimand strategy as for the secondary estimand for continuous endpoint at Week 12. It will be assumed that the same level of efficacy prior to the first ICE will continue, that is, last observation carried forward (LOCF) will be used for imputation.
- Population-level summary: Mean change from baseline to Week 24 in each intervention conditions
- Rationale for estimand: Refer to the rationale for the secondary estimand for continuous endpoints at Week 12.

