1.2. Study Design

Study KDAF is a Phase 2b, randomized, double-blind, placebo-controlled study to determine the appropriate dose and dosing frequency of peresolimab in adult participants with moderately-to-severely active RA.

[figure not shown]
This study includes a

- Period 1: screening period occurring approximately 1 to 42 days prior to Period 2
- Period 2: 12-week double-blind, placebo-controlled treatment period
- Period 3: 48-week double-blind treatment period, and
- Period 4: posttreatment follow-up period occurring 4 and 12 weeks from last treatment period visit (Week 60) or Early Discontinuation Visit.

See the Schedule of Activities (SoA) in the protocol for visit schedule, procedural and assessment details.

In the remainder of this statistical analysis plan (SAP), the first 12 weeks in Period 3 (that is, Weeks 12 to 24) will be referred as Period 3A and the last 36 weeks in Period 3 (that is, Weeks 24 to 60) as Period 3B for an analysis purpose. Combined Periods 2 and 3 will be referred as the Treatment Period (Weeks 0 to 60).

Figure KDAF.1.1 describes the study design for the treatment periods (Periods 2 and 3).

[figure not shown]

Abbreviations: CDAI = Clinical Disease Activity Index; SC = subcutaneous injection; Q4W = every 4 weeks; Q12W = every 12 weeks.

Note: At Week 12, participants receiving placebo Q4W will begin receiving either 400 mg or 1000 mg peresolimab Q4W. At Week 24, participants receiving 400 mg or 1000 mg peresolimab Q4W may be switched to Q12W dosing following assessment of CDAI scores.

Figure KDAF.1.1 Study design.

Participant population

Treatment period design

- 100 mg of peresolimab every 4 weeks (Q4W)
- 400 mg of peresolimab Q4W
- 1000 mg of peresolimab Q4W
- placebo Q4W up to Week 12 followed by 400 mg of peresolimab Q4W, and
- placebo Q4W up to Week 12 followed by 1000 mg of peresolimab Q4W.

Participants randomly assigned to placebo Q4W at Week 0

At Week 12, participants receiving placebo Q4W will begin receiving either 400 mg or 1000 mg peresolimab Q4W based on randomization at Week 0. Treatment assignment will be blinded, and the participants will continue their assigned peresolimab dose and dosing frequency until the end of the study.

Participants randomly assigned to 100 mg peresolimab at Week 0

Participants receiving 100 mg peresolimab will continue their assigned dose and dosing frequency throughout the duration of the treatment period. No changes will occur.

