1.2.1. Method of Assignment to Treatment

- 100 mg of peresolimab Q4W
- 400 mg of peresolimab Q4W
- 1000 mg of peresolimab Q4W
- placebo Q4W up to Week 12 followed by 400 mg of peresolimab Q4W, and
- placebo Q4W up to Week 12 followed by 1000 mg of peresolimab Q4W.

Participants who are randomized to either peresolimab 400 mg Q4W or peresolimab 1000 mg Q4W at Week 0 and meet CDAI \leq 10 at Week 24 will be randomly assigned to either Q4W or Q12W in the same dose level with a 1:1 ratio. Participants will be stratified by

• CDAI <2.8 vs 2.8 < CDAI <6 vs CDAI >6 at Week 24.

2. Statistical Hypotheses

The primary objective is to demonstrate that peresolimab is superior to placebo in achieving ACR20 at Week 12. Thus, the null hypothesis to be tested in relation to the primary estimand is:

There is no difference between peresolimab and placebo when evaluating the proportion of study participants with moderately-to-severely active RA achieving ACR20 at Week 12.

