2.1. Multiplicity Adjustment

Adjustment for multiple comparisons will not be employed in the analysis for this study.

3. Analysis Sets

Abbreviations: CDAI = Clinical Disease Activity Index; LDA = low disease activity; Q4W = every 4 weeks; Q12W = every 12 weeks; SC = subcutaneous.

Table KDAF.3.1. Treatment Groups and Comparisons for Each Study Period and Analysis Population

Study Period	Analysis	Treatment Group	Abbreviation	Inferential
	Population			Comparison
Double-blind, placebo- controlled treatment period (Period 2)	mITT Population Safety Population	Placebo SC Q4W ^a Peresolimab 100 mg SC Q4W Peresolimab 400 mg SC Q4W Peresolimab 1000 mg SC Q4W	PBO PER100Q4W PER400Q4W PER1000Q4W	PER100Q4W vs. PBO PER400Q4W vs. PBO PER1000Q4W vs. PBO
Double-blind treatment period Weeks 12 to 24 (Period 3A)	Maintenance Population	Placebo SC Q4W to Peresolimab 400 mg SC Q4W Placebo SC Q4W to Peresolimab 1000 mg SC Q4W Peresolimab 100 mg SC Q4W Peresolimab 400 mg SC Q4W Peresolimab 1000 mg SC Q4W	PBO/PER400Q4W PBO/PER1000Q4W PER100Q4W PER400Q4W PER1000Q4W	No Between-Treatment Comparison
Double-blind treatment period Weeks 24 to 60 (Period 3B)	Maintenance Primary Population	Peresolimab 400 mg SC Q4W Peresolimab 400 mg SC Q12W Peresolimab 1000 mg SC Q4W Peresolimab 1000 mg SC Q12W	PER400Q4W PER400Q12W PER1000Q4W PER1000Q12W	No Between-Treatment Comparison
	Maintenance Secondary Population	Peresolimab 400 mg SC Q4W Peresolimab 1000 mg SC Q4W	PER400Q4W PER1000Q4W	No Between-Treatment Comparison
	Maintenance Tertiary Population	Placebo SC Q4W to Peresolimab 400 mg SC Q4W Placebo SC Q4W to Peresolimab 1000 mg SC Q4W Peresolimab 100 mg SC Q4W	PBO/PER400Q4W PBO/PER1000Q4W PER100Q4W	No Between-Treatment Comparison
Combined Periods 2 and 3A (Weeks 0 to 24)	mITT Population	Placebo SC Q4W to Peresolimab 400 mg SC Q4W Placebo SC Q4W to Peresolimab 1000 mg SC Q4W Peresolimab 100 mg SC Q4W Peresolimab 400 mg SC Q4W Peresolimab 400 mg SC Q4W Peresolimab 1000 mg SC Q4W	PBO/PER400Q4W PBO/PER1000Q4W PER100Q4W PER400Q4W PER1000Q4W	No Between-Treatment Comparison
Treatment Period (combined Periods 2 and 3; Weeks 0 to 60)	Safety Population (for exposure table)	Peresolimab 100 mg SC Q4W Peresolimab 400 mg SC Q4W Peresolimab 1000 mg SC Q4W	PER100Q4W PER400Q4W PER1000Q4W PER400Q4W/Q12W	No Between-Treatment Comparison

Study Period	Analysis	Treatment Group	Abbreviation	Inferential
	Population			Comparison
	Safety	Peresolimab 400 mg SC Q4W to Peresolimab 400 mg SC	PER1000Q4W/Q12W	

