Short Form-36 version 2 health survey acute form (SF-36v2)	The SF-36v2 Acute measure is a subjective, generic, health-related quality of life instrument that is patient-reported and consists of 36 questions covering 8 health domains: physical functioning, bodily pain, role limitations due to physical problems, role limitations due to emotional problems, general health perceptions, mental health, social function, and vitality. Each domain is scored by summing the individual items and transforming the scores into a 0 to 100 scale with higher scores indicating better health status or functioning. In addition, 2 summary scores, the physical component	 Physical Functioning Role Physical Bodily Pain General Health Vitality Social Functioning Role Emotional Mental Health 2 component Scores: MCS Score PCS Score 		
	score (PCS) and the mental component score (MCS), will be evaluated based on the 8 SF-36v2 Acute domains (McHorney et al. 1993; Ware et al. 2007; Ware and Sherbourne 1992; Maruish 2011).	Change from baseline in 8 associated domain scores and 2 component scores	Calculated as: Observed value – baseline value	Missing if baseline or observed value are missing.

Abbreviations: PGA = physician's global assessment; PatGA = patient's global assessment; RA = rheumatoid arthritis; SF-36 = Short Form-36 health survey acute form; SJC = swollen joint count; TJC = tender joint count.

Table KDAF.4.2. Description of Efficacy and Patient Reported Outcome Analyses

Measure	Variable	Estimand	Analysis Method	Population	Comparison and Timepoint	Analysis Type
American College of Rheumatology (ACR)	ACR20	Composite	Logistic with NRI	mITT	PER100Q4W vs. PBO; PER400Q4W vs. PBO; PER1000Q4W vs. PBO; At Week 12 and all other scheduled visits in Period 2	Primary analysis is at Week 12.
		Composite	Descriptive statistics with NRI	Maintenance	No between-treatment comparison; At Week 24 and all other scheduled visits in Period 3A	Secondary analysis is at Week 24.
		Composite	Descriptive statistics with NRI	Maintenance Primary; Maintenance Secondary; Maintenance Tertiary	No between-treatment comparison; At Week 60 and all other scheduled visits in Period 3B	Secondary analysis is at Week 60.
	ACR50/70	Composite	Logistic with NRI	mITT	PER100Q4W vs. PBO; PER400Q4W vs. PBO; PER1000Q4W vs. PBO; At Week 12 and all other scheduled visits in Period 2	Secondary analysis is at Week 12.

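### The Week 24 re-randomisation to Q4W or Q12W is reported arm by arm; the visible plan gives no Q12W-minus-Q4W difference with its own confidence interval

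*SAP*

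**What the plan says.** The purpose is worded alike in both documents. Protocol 4.1 describes a "placebo-controlled study to determine the appropriate dose and dosing frequency of peresolimab", and SAP 1.2 repeats it: "to determine the appropriate dose and dosing frequency of peresolimab in adult participants".

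SAP 1.2.1 sets up the only randomised contrast of frequency. Participants originally assigned to 400 mg or 1000 mg Q4W who have CDAI of 10 or below at Week 24 "will be randomly assigned to either Q4W or Q12W in the same dose level with a 1:1 ratio", stratified by three bands: "CDAI <2.8 vs 2.8 < CDAI <6 vs CDAI >6 at Week 24".

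Table KDAF.3.1 (SAP 3) lists the resulting groups for Period 3B under the Maintenance Primary Population as "PER400Q4W PER400Q12W PER1000Q4W PER1000Q12W". Its Inferential Comparison column reads "No Between-Treatment Comparison". Table KDAF.4.2 (SAP 4.5) carries the same rule in each visible Week 60 row, with descriptive statistics as the method: "No between-treatment comparison; At Week 60 and all other scheduled visits in Period 3B".

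The estimand agrees with the tables. For categorical endpoints SAP 1.1 gives the population-level summary as "Proportion of participants achieving response at Week 24 (or Week 60) in each dosing regimen of peresolimab". SAP 4.4.3.2 then lists counts, rates and 95% CIs by treatment group for binary endpoints, and means, standard deviations and ranges for continuous ones. No difference between groups appears.

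**The concern.** A second randomisation is worth its complexity because it supports a comparison between concurrent groups that differ only in dosing interval. Participants enter it on a single CDAI value at or below a cut-off, so some will rise above the cut-off later on either schedule. The randomised Q4W group shows how much of that would have happened anyway, and the between-group difference is the quantity that uses it.

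Under the visible plan that difference is left to the reader. Four separate rates with four separate intervals will be compared by eye, without the randomisation strata and without combining the two doses. Overlapping single-arm intervals are easily taken to mean that the longer interval loses nothing, when the data may be unable to exclude a large loss.

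**Working it through.** **Is a frequency effect estimated elsewhere in the visible plan?**

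- The Bayesian dose-response models (SAP 4.2 and 6.9.2) are functions of dose alone. At Week 12, the time of the primary endpoint, every active arm is on Q4W, so they carry no information on interval.
- Exposure-response modelling (Protocol 9.3.6, SAP 4.7.3) is optional. It could bear on frequency indirectly, but it does not analyse the randomised groups.
- The Week 60 estimands (SAP 1.1) and outputs (SAP 4.4.3.2) are per regimen.

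The difference is therefore absent from everything that can be read.

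**Check of the plan's own figure.** SAP 5 gives approximate arm sizes of 60 (100 mg), 120 (400 mg), 120 (1000 mg) and 120 (placebo). 60 + 120 + 120 + 120 = 420, the stated total. No size is visible for the Q4W and Q12W groups, and response rates and power are redacted.

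**Precision of the missing difference.** Assumptions, not document figures:
- 20% to 50% of the 120 per dose are re-randomised. This is a net share, after attrition and after excluding those barred from switching by earlier rescue.
- 75% on Q4W and 60% to 75% on Q12W are in low disease activity at Week 60.

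Group size per frequency within a dose is n = 120 × share / 2, which gives 12 (20%) to 30 (50%).

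The 95% CI half-width is 1.96 × √(p₁(1−p₁)/n + p₂(1−p₂)/n).

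| Case | n per group | Within a dose | Two doses pooled (÷ √2) |
|---|---|---|---|
| 20% re-randomised; 75% vs 60% | 12 | 1.96 × √(0.1875/12 + 0.24/12) = 37.0 points | 26.2 points |
| 50% re-randomised; 75% vs 75% | 30 | 1.96 × √(2 × 0.1875/30) = 21.9 points | 15.5 points |

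Pooling narrows the interval by 1 − 1/√2, about 29%.

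**Power, for context.** For an assumed 80% versus 60%, two-sided 5%, power is about 18% to 39% within a dose and 32% to 67% pooled. Reaching 80% power would take 82 per group. The contrast suits estimation, not a test.

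**What the reader would and would not see.** Take 30% re-randomised (n = 18 per group), with 13 of 18 responders on Q4W and 10 of 18 on Q12W.
- Planned output: 72% (52 to 93) and 56% (33 to 79). The intervals overlap.
- Omitted output: Q12W minus Q4W = −17 points (95% CI −48 to +14). A large loss on the longer interval is not excluded.

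**Why continuous endpoints need separate care.** SAP 4.1 defines LOCF as carrying the last nonmissing value up to Week 24, while Table KDAF.4.2 applies LOCF at Week 60. Read literally, a missing Week 60 value would be filled with one from no later than Week 24, before the two schedules could diverge. That would pull a Q12W-minus-Q4W mean difference toward zero. Binary endpoints avoid this: use of rescue, including when a Q12W participant returns to Q4W with rescue (SAP 1.2), counts as nonresponse under the composite strategy, and remaining missing values are nonresponse under NRI.

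**The case against.** The best defence is that the plan is consistent with itself. The visible objectives table has no row comparing Q4W with Q12W. The Week 24 and Week 60 secondary objective is worded without a comparator, unlike the Week 12 one, and its estimand and analysis follow suit. A reader might infer that a formal frequency objective has been left unanalysed. The documents do not support that: frequency appears as design purpose, and the exploratory objectives are not visible.

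A reader might also infer that no frequency analysis of any kind exists, or that the trial will give no information on frequency. Neither can be claimed. The text of SAP 4.5 and some rows of Table KDAF.4.2 are removed, and the separate PK/PD plan is not available. The concurrent Q4W group is reported beside Q12W, so the point difference follows by subtraction, and because allocation is randomised 1:1 an unstratified difference is not biased. What is missing is a prespecified difference with its own interval.

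Small groups make descriptive reporting defensible in Phase 2b. That argues against a test or a claim, but an interval is how small numbers should be shown. Two practical points stand. At 12 per group, three CDAI strata leave about 4 per cell, so full stratification may not be feasible. Pooling averages over two doses whose frequency effects may differ. Finally, the population definitions in SAP 3 are not visible, so identifying the Maintenance Primary Population with the re-randomised participants is an inference from its four listed groups.

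**Conclusion.** The point holds in this form. The study is described as determining dosing frequency and randomises to it, yet the visible plan rules out a between-group comparison in that population. The result is per-arm summaries without a Q12W-minus-Q4W difference and confidence interval. This is a stated rule, not missing detail.

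The difference is estimable but imprecise: half-widths of about 22 to 37 points within a dose and 16 to 26 pooled. Those figures rest on the assumed share re-randomised and the assumed maintenance rates. The finding itself rests on no numeric assumption. It does not affect the primary endpoint or any Week 12 comparison. It is a change the sponsor should make, or else give a reason for not estimating the randomised contrast.

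**What to change.** For the Maintenance Primary Population only:

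1. In Tables KDAF.3.1 and KDAF.4.2, replace the no-comparison entry for the Week 60 binary secondary endpoints with PER400Q12W vs PER400Q4W and PER1000Q12W vs PER1000Q4W. Report the difference in proportions with 95% CI under the existing composite strategy and NRI.
2. Adjust for the Week 24 CDAI randomisation strata where cell sizes allow, with a stated fallback to an unadjusted difference.
3. Add a dose-stratified pooled Q12W-minus-Q4W estimate as supportive, noting that it averages over the two doses.
4. Label all of this as estimation, with no multiplicity claim.
5. Align the Week 60 categorical estimand summary (SAP 1.1), SAP 4.4.3.2 and the statement of no changes in SAP 4.9.
6. Add differences in mean change for continuous endpoints only after the LOCF rule in SAP 4.1 is reconciled with the Week 60 analyses, so that values from before re-randomisation are not carried into the contrast.

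Leave the Maintenance Secondary and Tertiary rows without comparison, since those groups are not randomised to frequency.

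The cost is SAP wording and a few table columns, with no new participants, visits or data. Protocol 9.3.1 lets non-principal analysis changes be described in the SAP and study report. Timing matters: SAP version 3 is signed December 2024 and was to precede the final lock. If a further version before that lock is not possible, the contrast should be reported as an addition to the approved plan. The main downside is wide intervals, which the report should present as such.

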4.6. Safety Analyses

All safety data will be descriptively summarized by treatment groups and by treatment periods. Safety data for Period 2, Period 3A, and Period 3B will be analyzed based on the Safety Population, Maintenance Population, and Maintenance Primary/Secondary/Tertiary Population, respectively, as defined in Section 3. For Period 3B based on Maintenance Primary/Secondary/Tertiary Population, the treatment groups will be combined and not be separated by populations. Patients will be summarized according to the treatment to which they were assigned at Week 24. Safety summaries will be presented by treatment arm as defined in Table 3.1. The safety analyses include adverse events (AEs), safety in special groups and circumstances, including, but not limited to, adverse events of special interest, laboratory analytes, and vital signs.

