Participants randomly assigned to 400 mg or 1000 mg peresolimab at Week 0

Participants receiving 400 mg or 1000 mg peresolimab will continue their assigned dose and dosing frequency until Week 24. At Week 24, participants may be switched to every 12 weeks (Q12W) dosing following assessment of CDAI scores, unless they received rescue medication prior to Week 24.

Abbreviations: CDAI = Clinical Disease Activity Index; Q4W = every 4 weeks; Q12W = every 12 weeks.

- At Week 24 using the Visit 9 (Week 24) assessments, a participant does not achieve CDAI LDA
 - o These participants will receive permitted rescue therapy.
- For participants that achieved CDAI LDA at Week 24, those who do not maintain CDAI LDA for 2 consecutive visits after Week 24
 - o These participants will receive peresolimab Q4W and permitted rescue therapy.
 - If a participant is currently receiving peresolimab Q4W, they will continue receiving peresolimab Q4W.

• If a participant is currently receiving peresolimab Q12W, they will switch to peresolimab O4W.

[figure not shown]
Escape criteria after Week 24

A participant not achieving ≥20% improvement in both TJC and SJC at 2 consecutive visits after Week 24, while receiving rescue therapy, should be permanently discontinued from study intervention. Participants may continue in the study and receive additional standard of care therapies at the investigator's discretion.

Participation in an open-label extension study

If an open-label extension study is enrolling at the time the participant completes Visit 18 (Week 60), they will be given the opportunity to enroll in that study.

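### Period 3B safety tables pool re-randomised and non-re-randomised participants in the 400 mg and 1000 mg Q4W columns but not in the Q12W columns, so no readable safety summary shows the randomised frequency groups like for like

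*SAP*

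**What the plan says.** SAP Section 4.6 analyses Period 3B safety on the three Maintenance populations together: "the treatment groups will be combined and not be separated by populations". It adds "Patients will be summarized according to the treatment to which they were assigned at Week 24" and "Safety summaries will be presented by treatment arm as defined in Table 3.1", meaning Table KDAF.3.1 in SAP Section 3.

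For Period 3B that table lists:

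- Maintenance Primary: "PER400Q4W PER400Q12W PER1000Q4W PER1000Q12W"
- Maintenance Secondary: "Peresolimab 400 mg SC Q4W Peresolimab 1000 mg SC Q4W"
- Maintenance Tertiary: the two placebo-to-peresolimab groups and 100 mg Q4W

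Under SAP Section 1.2.1, participants who started on 400 mg or 1000 mg and have CDAI of 10 or less at Week 24 "will be randomly assigned to either Q4W or Q12W in the same dose level with a 1:1 ratio". SAP Section 1.2 describes the switch to Q12W as possible "unless they received rescue medication prior to Week 24", and says participants not in CDAI low disease activity (LDA) at Week 24 receive rescue therapy. For those who later lose LDA at two consecutive visits: "If a participant is currently receiving peresolimab Q12W, they will switch to" Q4W, with rescue.

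Table KDAF.3.1 plans no between-treatment comparison in Period 3B, and Section 4.6 makes all safety summaries descriptive. For efficacy in the same period, Table KDAF.4.2 names the three Maintenance populations separately.

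**The concern.** Pooling by assigned treatment is harmless when every column draws on the same kinds of participant. Here it does not. The Secondary population adds people to the 400 mg and 1000 mg Q4W columns and nobody to the Q12W columns. On the design text, those added are mainly participants not in LDA at Week 24 or already rescued. They probably have more active disease and more concomitant treatment in Period 3B, both plausible influences on adverse events such as infection, which Section 4.6.2 lists as an event of special interest.

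The study sets out to determine dosing frequency as well as dose (SAP Section 1.2). The Week 24 re-randomisation is the only randomised source of Q4W versus Q12W safety data in the readable design, and it is stratified by CDAI so that disease activity is balanced. The pooled columns lose that balance. A gap between them, or the absence of one, cannot be attributed to frequency, and the direction of any distortion is unknown.

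**Working it through.** **Column make-up.** Setting Section 4.6 beside Table KDAF.3.1, each dose's pooled Q4W column is Primary Q4W plus Secondary Q4W; each Q12W column is Primary Q12W alone. The 100 mg column is unaffected. The placebo-switch groups most naturally keep their own columns, as in the table, though the word for pooling leaves this open. If they joined the Q4W columns, the mixing would increase.

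**Other safety displays.** None of the readable ones separates the groups.

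- The Weeks 0 to 60 tables distinguish Q4W from Q4W/Q12W, but their Q4W columns also include participants not re-randomised, among them any who stopped before Week 24.
- The follow-up period has one Q4W and one Q12W column per dose.
- Section 4.7.2 plans no safety subgroup analysis unless a relevant finding arises.
- By-patient listings are not group summaries.

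**Inputs for size.** SAP Section 5 gives about 120 participants each on 400 mg and 1000 mg at Week 12. The stated group sizes reproduce the stated total: 60 + 120 + 120 + 120 = 420. The re-randomised share r, the event rates and the dropout are not given, so what follows is illustration.

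**Formulas, per dose, no dropout.**

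- Q12W column = 120r/2
- Q4W column = 120r/2 + 120(1 − r)
- Share of the Q4W column never randomised to frequency = (1 − r)/(1 − r/2)
- Apparent Q4W versus Q12W gap with no frequency effect = share × assumed difference in adverse event rate between the two kinds of participant

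| Assumed r | 20% | 30% | 40% | 50% | 70% |
|---|---|---|---|---|---|
| Re-randomised | 24 | 36 | 48 | 60 | 84 |
| Q12W column | 12 | 18 | 24 | 30 | 42 |
| Not re-randomised | 96 | 84 | 72 | 60 | 36 |
| Q4W column | 108 | 102 | 96 | 90 | 78 |
| Never randomised to frequency | 88.9% | 82.4% | 75.0% | 66.7% | 46.2% |
| Gap for a 10-point difference | 8.9 | 8.2 | 7.5 | 6.7 | 4.6 |

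A 5-point difference halves each gap: 4.4 points at 20%, 2.3 at 70%. The never-randomised share falls to one half only at r = 2/3.

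**Dropout.** Equal loss in all groups leaves the shares unchanged. If 15% (18 of 120) leave before Week 24, all of whom would otherwise not have been re-randomised, then for r = 20/30/40/50%:

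- 78/66/54/42 of the not-re-randomised remain
- the Q4W columns hold 90/84/78/72
- the shares are 86.7/78.6/69.2/58.3%, and the 10-point gaps 8.7/7.9/6.9/5.8

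**Sampling noise.** At an assumed 40% event risk, the 95% half-width of the pooled difference is:

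- r = 20%: 1.96 × √[0.24 × (1/108 + 1/12)] = 29 points
- r = 50%: 1.96 × √[0.24 × (1/90 + 1/30)] = 20 points

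For a Primary-only display with n per column, it is 1.96 × √(2 × 0.24/n): 39/32/28/25 points at n = 12/18/24/30. The chance that an event with a true 5% risk is absent from such a column is 0.95ⁿ: 54/40/29/21%.

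**The case against.** The strongest reply is that this is a deliberate, disclosed presentation choice. The pooling sentence was added in SAP Version 2 and logged as a clarification, the column rule is stated, and no Period 3B comparison is planned, so the plan draws no inference for the pooling to bias. The readable objectives include no safety-by-frequency objective. All this stands as a limit on severity: there is no contradiction and no test is harmed. It does not answer the interpretive point, because readers will compare adjacent frequency columns in a study that aims to choose a frequency.

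Second, the population definitions in SAP Section 3 are not readable, so the make-up of Secondary is inferred. That its members were not randomised to frequency is a strong inference, since it has no Q12W group. Exactly who they are is less certain: Section 1.2 excludes those rescued before Week 24 from Q12W, while Section 1.2.1 states only the CDAI condition.

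Third, the event-rate differences are assumed, and the illustrated gap is about a third of the pooled table's own sampling half-width. That is fair, and it shrinks the illustration. The difference in make-up between the columns depends on none of these rates, and a systematic difference in patient mix is a different problem from imprecision.

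Fourth, Primary-only columns would be small and, because some Q12W participants later return to Q4W, would compare assigned strategies rather than sustained exposure. Both are true. The added display would supplement the pooled tables, and the view could also be produced later if a signal appeared, but it is not planned now.

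**Conclusion.** The concern holds. As planned, the Period 3B 400 mg and 1000 mg Q4W safety columns combine randomised and non-randomised frequency groups, the Q12W columns do not, and no other readable safety summary offers the randomised contrast. At an assumed 20 to 50% re-randomised and 120 per dose without dropout, 89 to 67% of each Q4W column was never randomised to frequency; at 70% it is 46%. The spurious gap ranges from 8.9 points (20% re-randomised, 10-point case-mix difference) to 2.3 points (70%, 5-point difference). These sizes rest entirely on assumed rates. The structural finding rests on Section 4.6, Table KDAF.3.1 and the inferred make-up of Secondary. It is a limit on interpretation that should be corrected. Efficacy is not affected, because Maintenance Primary is already listed separately there.

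**What to change.** Keep the pooled Period 3B safety tables and amend SAP Section 4.6 as follows:

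- Add key safety summaries (adverse event overview, serious adverse events, adverse events of special interest) for the Maintenance Primary population alone, in its four randomised columns.
- State in one sentence whether the two placebo-switch groups keep their own columns, as Table KDAF.3.1 implies.
- Footnote the pooled tables: the 400 mg and 1000 mg Q4W columns include participants not randomised to frequency, and the Q12W columns follow Week 24 assignment and may include participants later switched to Q4W.

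No between-group test is requested and no treatment rule changes. The cost is a few tables, a sentence and a footnote, using a population flag the SAP already applies to efficacy. The downside is imprecision: the small columns give a like-for-like view but cannot rule out uncommon events, and the text should say so.

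### Period 3B safety is tabulated by Week 24 assignment, so the Q12W columns include events that occurred after participants had returned to Q4W dosing, and no display shows safety on Q12W itself

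*SAP*

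**What the plan says.** Period 3B is defined in SAP 1.2 as "the last 36 weeks in Period 3 (that is, Weeks 24 to 60) as Period 3B". Under SAP 1.2.1, participants on 400 mg or 1000 mg whose CDAI is 10 or below at Week 24 "will be randomly assigned to either Q4W or Q12W in the same dose level with a 1:1 ratio".

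SAP 1.2 then gives a rule for participants who had LDA at Week 24 and lose it, namely "those who do not maintain CDAI LDA for 2 consecutive visits after Week 24". The consequence is: "These participants will receive peresolimab Q4W and permitted rescue therapy". For the longer interval it is explicit: "If a participant is currently receiving peresolimab Q12W, they will switch to" Q4W.

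SAP 4.6 sets the attribution rule for Period 3B safety: "Patients will be summarized according to the treatment to which they were assigned at Week 24". It takes its arms from Table KDAF.3.1. For the re-randomized participants that table has four Period 3B groups: Q4W and Q12W at each of the two doses. It has no group for participants who went from Q12W back to Q4W. SAP 4.6 also merges the Maintenance Primary, Secondary and Tertiary Populations for the Period 3B safety tables.

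The rule in SAP 4.1 on data after rescue covers efficacy only. The visible text contains no safety summary by regimen received and no split of events or time at the return to Q4W.

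**The concern.** Dosing frequency is part of the study's stated aim in both documents (Protocol 4.1, SAP 1.2), and the Week 24 re-randomization is the part of the design that informs it. A reader who opens a Period 3B table at the PER400Q12W or PER1000Q12W column will take it as the safety record of 12-weekly dosing. Under the planned rule it is the record of being assigned to 12-weekly dosing, including any later time on 4-weekly dosing. Among the re-randomized participants the return rule moves people only from Q12W to Q4W. The mixing therefore makes the Q12W column more like Q4W, and more so as more Q12W participants lose response. Without a further display or a count of returners, nobody can tell how much of the Q12W record was collected on Q12W.

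**Working it through.** **Inputs**
- Period 3B: Weeks 24 to 60 (SAP 1.2).
- First visit of the interval: "At Week 24 using the Visit 9 (Week 24) assessments" (SAP 1.2).
- Last visit: Visit 18 at Week 60 (SAP 1.2; Protocol 6.6).
- Trigger: LDA not maintained at two consecutive visits after Week 24 (SAP 1.2).
- Doses are given at site visits (Protocol 6.1).

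**Plan's own figure.** 60 − 24 = 36 weeks, which reproduces the stated length of Period 3B.

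**Visit spacing.** 36 / (18 − 9) = 4 weeks if visits are evenly spaced. The Schedule of Activities is not readable, so this is an assumption, although 4-weekly dosing at visits fits it. Visits after Week 24 then fall at Weeks 28, 32, …, 60.

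**Earliest return.** The second visit after Week 24 is Week 32. Time left in Period 3B is 60 − 32 = 28 weeks, and 28/36 = 0.778. If the change takes effect one visit later, it is 60 − 36 = 24 weeks, and 24/36 = 0.667.

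| Return at week | Weeks left to Week 60 | Share of 36 weeks |
|---|---|---|
| 32 | 28 | 0.778 |
| 36 | 24 | 0.667 |
| 40 | 20 | 0.556 |
| 44 | 16 | 0.444 |
| 48 | 12 | 0.333 |
| 52 | 8 | 0.222 |
| 56 | 4 | 0.111 |

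**Doses received.** Assume doses at visits from Week 24 to Week 56. Uninterrupted Q12W gives 3 doses (Weeks 24, 36, 48). Uninterrupted Q4W gives 9 (Weeks 24, 28, …, 56). A participant who returns at Week 32 gets 1 at Week 24 plus 7 at Weeks 32 to 56, so 8. That participant is one dose short of the full Q4W schedule, but all 36 weeks stand under Q12W.

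**Arm level.** The share of Period 3B person-time in a Q12W column spent after return is p × r / 36. Here p is the proportion returning and r is their mean remaining weeks; all participants are taken as followed to Week 60. The documents give neither p nor r. The only bounds are 0 (nobody returns) and 0.778 (everyone returns at Week 32), so no central value is offered.

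**Which outputs are affected.** The attribution rule acts on outputs produced for Period 3B:
- by-period adverse event tables;
- the hematology, lipid and creatinine shifts that SAP 4.6.3 asks for by treatment period;
- vital-sign summaries with a baseline for each period (SAP 4.6.5).

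It does not reach outputs built on Weeks 0 to 60. There, Table KDAF.3.1 labels the columns PER400Q4W/Q12W and PER1000Q4W/Q12W.

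**The case against.** The strongest reply is that summarizing by assignment is a legitimate choice. The Week 24 split is randomized, return to Q4W on loss of response is part of the Q12W strategy, and keeping people where they were assigned preserves the randomized groups. That stands as a reason to keep the table. It is weaker than it looks, because SAP 4.6 merges the maintenance populations. The Q4W groups at 400 mg and 1000 mg appear in both the Primary and the Secondary Population, so the planned Q4W column is apparently not confined to re-randomized participants. The population definitions in SAP Section 3 are not visible, so this cannot be confirmed, and they could hold text that bears on the point.

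Four stronger readings are tempting, and the documents do not support them.
- **Overall exposure and exposure-adjusted rates are reported as Q12W.** Table KDAF.3.1 places the exposure table in the Weeks 0 to 60 row, whose columns are openly mixed. The exposure-adjusted rates in SAP 4.6.2.2, 4.6.2.5 and 4.6.2.6 are for the Treatment Period or for all time on peresolimab.
- **A comparison is biased.** Table KDAF.3.1 plans no between-treatment comparison in Period 3B, and safety is descriptive throughout.
- **Rescue-drug events are wrongly charged to Q12W alone.** Q4W participants who lose LDA also receive rescue (SAP 1.2). Only the change in dosing frequency is specific to Q12W.
- **Returners could count as Q12W responders at Week 60.** SAP 1.2 pairs return with rescue. Rescue is already an intercurrent event leading to nonresponse, and SAP 1.1 applies that strategy at Week 60.

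By-patient listings of adverse events, serious adverse events and exposure are planned, so the information is not lost. A listing, however, does not give a rate or a count by regimen received.

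**Conclusion.** The point holds as a limit on interpretation. The Period 3B Q12W safety columns describe assignment to Q12W and cannot, as planned, describe safety while dosed Q12W. For one participant up to 28 of 36 weeks (78%) can be Q4W time, or 24 of 36 (67%) if the return takes effect one visit later. Both figures assume 4-weekly visits, and both are maxima for the earliest possible returner, not averages. The effect on a whole arm is unknown because the documents give no expected number of returners. No test, estimand or dosing rule is in error. A supplementary display is worth adding because it is cheap and bears on a stated aim of the study.

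**What to change.** Keep the as-assigned Period 3B table. In SAP 4.6 and Table KDAF.3.1, add a supplementary Period 3B safety display restricted to participants re-randomized at Week 24:

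- **Q12W arms:** count events and matching Period 3B person-time up to the earlier of rescue start and the first dose after return to Q4W.
- **Q4W arms:** apply the same cut-off at rescue start, so that time after loss of response is not removed from one side only. Time after the cut-off stays visible in the as-assigned table.
- **Separate column:** show later Q12W-arm events and time under 'Q12W returned to Q4W', by dose.
- **Counts:** for each Q12W arm, report the number who returned and their Q4W person-time. If only one item is added, it should be this one.

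The cost is SAP wording, two derived dates per participant (rescue start and first dose after return) and one extra column per dose. Study conduct does not change. If the final database is already locked, the display can still be reported, labelled as supplementary.

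There are two drawbacks. The on-regimen columns are censored by loss of response, so they describe selected time. Events soon after return may also still reflect Q12W dosing. For both reasons the display supplements the as-assigned table and does not replace it.
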